The neuropsychological assessment in the proposed study is a unique approach to further characterize domain-specific cognitive function as a predictor of the ability to use exercise-based behavioral therapy. The baseline neuropsychological battery will provide additional domain-specific measures of cognitive function (SRTT, executive function, word retrieval) that will be analyzed in the context of the ability to learn and implement the exercise-based behavioral strategy. These preliminary data will provide further evidence to support or refute the hypothesis that learning the PFME-based adaptive strategy is a procedural task and that implementation of the task uses implicit memory rather than explicit memory systems. Further, because several of the selected tests have neuroanatomical correlates, these data could support the design of future studies involving functional brain imaging to understand mechanisms of learning in the context of neurodegenerative disease, thus building on imaging studies in non-PD populations with OAB^{15,16}.

Measures: Participants in both groups will complete the SRTT (task of procedural learning) in addition to a neuropsychological battery that will include evaluations of executive function and explicit memory at baseline. These assessments mirror the evaluation included in the BETTUR2 study, which will ultimately increase the power of the evaluation to determine mediators impacting implementation of behavioral therapy for urinary symptoms in persons with PD.

Data Analysis: The analysis for Aim 2a will determine if baseline cognitive function scores mediate successful outcome in the behavioral therapy group. Based on previously published research and our pilot studies, successful implementation of behavioral therapy will be defined as achieving at least a 2-point reduction in the ICIQ-OAB symptom score^{24,61,64}. Cognitive function will be evaluated as a continuous and categorical measure (MoCA 18-24 vs 25-30).

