To explore other potential characteristics of successful behavioral therapy implementation, we will examine baseline characteristics that differ between those in the behavioral therapy group who demonstrate at least a 2-point improvement (reduction) in ICIQ-OAB symptom score versus those who report less improvement. Baseline characteristics will include gender, age, PD severity as measured by the MDS-UPDRS motor part 3 score (mild vs. moderate), depression as well as the pre-specified measures of cognitive function (SRTT and Wisconsin Card Sort Test). Baseline characteristics will be compared using chi-square or t-tests as appropriate.

We will examine the correlation between cognitive function tests of procedural learning and executive function with change in ICIQ-OAB score after behavioral therapy. Performance on the SRTT will be assessed as the mean change in time (milliseconds) between random and sequential tasks. Performance on the Wisconsin Card Sort Test will be assessed using the perseverative errors score. We will correlate these measures with the change in ICIQ-OAB score between baseline and 12-weeks post-randomization.

Baseline characteristics which are significantly associated with successful implementation of behavioral therapy will be included as part of a multivariable logistic regression model including SRTT performance, Wisconsin Card Sort Test perseverative errors score in order to determine if these cognitive domains are important in the central nervous system control of OAB symptoms in response to behavioral therapy.

Aim 2b: Compared to exercise therapy, does anticholinergic drug treatment for urinary symptoms worsen executive function and PD motor symptom severity?

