Regardless of whether behavioral therapy proves to be inferior or non-inferior to drug therapy, understanding the potential association of drug therapy with cognition or PD motor symptom severity are important factors for patients and providers to determine next steps for treatment⁶⁹.

Measures: Participants in both groups will complete a baseline and 12-week neuropsychological battery as previously described including the MoCA test, SRTT, CERAD Word List subtest, Nonverbal/Spatial Reminding Test, Wisconsin Card Sort Test, and the Subject Ordered Pointing task. We will use the Anticholinergic Risk Scale⁴⁷ to calculate an overall anticholinergic drug score for participants in both groups based on medications listed at the randomization visit as a potential effect modifier. The MDS-UPDRS will be repeated at the 12-week visit. Thus, the behavioral therapy group will serve as a control group to assess the potential impact of solifenacin drug therapy on domain-specific cognitive function and PD motor symptom severity.

Data Analysis: [The analysis for aim 2b will generate data informing how central cognitive control of sensory integration and motor function are involved in the response to drug therapy.] Baseline and 12-week post-randomization cognitive tests will be evaluated using paired t-tests to assess for change within the drug group and two-sample t-tests for differences across groups (the behavioral therapy group will serve as a control for this analysis). Because cognitive impairment in PD most often manifests as impaired executive function, we will focus on tests of this domain, such as the Wisconsin Card Sort Test or the Subject Ordered Pointing Task in our evaluation of impact on cognition. The clock-draw test, as a component of the MoCA, is another assessment of executive function that is often performed in clinical practice. If changes are noted on domain-specific assessments of the neuropsychological battery, we will also examine correlation with clock draw scores obtained through the MoCA test. The Anticholinergic Risk Scale will be assessed based upon medications at randomization. The Anticholinergic Risk Scale score will be included in a multivariable model including baseline characteristics associated with changes in cognitive function in bivariable analyses.

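### The only adjusted Aim 2a model dichotomizes the response in about 40 people and picks its covariates by univariable significance; a fixed linear model would be more powerful and more reliable

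*Combined protocol and SAP*

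**What the plan says.** The Aim 2a Data Analysis text sets the response: "successful implementation of behavioral therapy will be defined as achieving at least a 2-point reduction in the ICIQ-OAB symptom score". Responders and non-responders within the behavioral arm are then compared on baseline characteristics. The list is "Baseline characteristics will include gender, age, PD severity as measured by the MDS-UPDRS motor part 3 score (mild vs. moderate), depression", together with the two prespecified cognitive measures, SRTT and the Wisconsin Card Sort Test. The screen is by simple tests: "Baseline characteristics will be compared using chi-square or t-tests as appropriate".

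The result of that screen decides the adjusted model: "Baseline characteristics which are significantly associated with successful implementation of behavioral therapy will be included as part of a multivariable logistic regression model". The same sentence names the two cognitive measures as part of it: "multivariable logistic regression model including SRTT performance, Wisconsin Card Sort Test perseverative errors score". They therefore enter whatever their own univariable result.

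A continuous analysis is also planned for SRTT and card-sort perseverative errors: "We will correlate these measures with the change in ICIQ-OAB score between baseline and 12-weeks post-randomization". No adjustment is described for it.

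For Aim 2b, the Anticholinergic Risk Scale score goes into a "multivariable model including baseline characteristics associated with changes in cognitive function in bivariable analyses". That response is change in cognitive function and is not dichotomized.

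For neither screen do the documents give a significance threshold, a limit on the number of variables, shrinkage or validation. No sample size or power is stated for Aim 2.

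**The concern.** Choosing covariates by their significance in the sample that is then modelled has two costs. Irrelevant characteristics get in by chance and, having been selected for a large observed association, look important. Genuine confounders are left out when the sample is too small to detect them. The final confidence intervals take no account of the selection.

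Cutting a 0–16 score at a 2-point change adds a separate cost: it discards information on how much each person improved, in a group that is already small. Baseline ICIQ-OAB is missing from the candidates. Participants are selected on a score of at least 7, so some regression to the mean is expected and baseline should be related to change.

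The stake is the stated purpose of this model: to determine whether procedural learning and executive function matter for response to behavioral therapy. The primary non-inferiority analysis is not affected.

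**Working it through.** **Inputs from the documents.** 90 randomized and 80 completing, so about 40 completers per arm (Power Analysis, Table 6 at SD 2.0 and a 15% margin). Expected reduction is 2–3 points. Four characteristics are screened (gender, age, motor severity, depression) and two predictors are forced in (SRTT, card-sort).

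**Assumptions, not in the documents.** Screening at two-sided 0.05; change with mean 2.5 and SD 2.0 (range 2–3); true correlations of 0.2 to 0.4.

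**The figure of 40.** This is the plan's only relevant figure, and here it serves only as a head count. With margin 0.15 × 8.1 = 1.215, the t-based calculation for 85% power gives 40 per arm at one-sided 0.05, but 50 at the stated one-sided 0.025. That is a separate matter and does not alter this point.

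**1. Noise entering.** 1 − 0.95⁴ = 18.5% for at least one of four irrelevant covariates (17–19% in simulation).

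**2. Confounder missed.** For a covariate correlated 0.4 with the change, the responder t-test has about 53% power, so it is missed about 47–48% of the time. If it is also correlated 0.4 with SRTT, and SRTT has no effect of its own, the screened model leaves a small bias in the SRTT term: median log odds ratio 0.09 instead of 0.

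**3. Model size.** Responder share = Φ((2.5 − 2)/2) = Φ(0.25) = 0.60, so about 24 responders and 16 non-responders. With all six terms, 16/6 = 2.7 in the smaller class per term; with the two forced terms only, 16/2 = 8. Over mean 2–3 and SD 2–3 the smaller class is about 12–20, giving 2.0–3.3 and 6–10 respectively.

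**4. Cost of the cut.** A correlation r with a normal score becomes r × φ(0.25)/√(0.599 × 0.401) after dichotomizing. The factor is 0.387/0.490 = 0.79, so r = 0.40 becomes about 0.32. Squared, the factor is 0.62: 40 people count as about 25. By Fisher's z:
- continuous: atanh(0.40) × √37 − 1.96 = 0.62, power about 73%;
- cut: atanh(0.316) × √37 − 1.96 = 0.03, power about 51%.

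Simulation (10,000 trials, n = 40) agrees:

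| True r | Single predictor, cut | Single predictor, continuous | SRTT in screened logistic model | SRTT in fixed six-term linear model |
|---|---|---|---|---|
| 0.2 | 16% | 24% | – | – |
| 0.3 | 32% | 48% | 28% | 42% |
| 0.4 | 53% | 75% | 48% | 68% |

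A separate simulation put the screened logistic model at about 45% for r = 0.4, and fixed linear models at 68–76%. The six-term linear model holds SRTT, card-sort and all four candidates, without baseline ICIQ-OAB. The gain from adding baseline is not quantified, because the documents give no baseline–follow-up correlation.

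**5. Effect of screening on the forced terms.** Under the null, the SRTT test in the screened model rejects 4.3% of the time (4.6% with the confounder in step 2). At r = 0.3 its mean log odds ratio is 0.60 against a large-sample value of 0.51. The two-term model without any screening gives 0.59. The excess, 0.60/0.51 = 1.2-fold, is therefore ordinary small-sample logistic bias and not a product of the screening.

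**The case against.** The best defence is that the two predictors of interest are protected from the screen. A reader might infer that screening exaggerates the cognitive estimates more than twofold. Inflation of that kind does occur for a covariate that must reach p < 0.05: one with a true odds ratio of 1.39 per SD shows a median of 2.47 when it passes. But SRTT and card-sort do not have to pass. Steps 2 and 5 show that their error rate holds and that the bias from a missed confounder is small. This part of the defence stands.

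Second, the plan already contains a continuous analysis of SRTT and card-sort, with about 74–75% power at r = 0.4. It would be wrong to say that Aim 2a as a whole loses power. That also stands, but the correlation is unadjusted and cannot replace the adjusted model.

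Third, six terms is the worst case. If all four candidates are irrelevant, none enters about 81% of the time, and the model has two terms. This stands for model size; the loss from the cut remains.

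Fourth, it is tempting to say that a low baseline prevents a 2-point fall. It does not: everyone enters at 7 or more on a scale that goes down to 0. The case for adjusting for baseline rests on regression to the mean and precision.

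Last, the responder comparison is introduced as exploratory and the data are called preliminary. This limits the weight of the point. However, the text gives the logistic model the task of determining whether these cognitive domains matter, under a named specific aim.

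**Conclusion.** The point holds for the adjusted Aim 2a model. Under the stated assumptions, its power for SRTT at r = 0.4 is about 45–48%, where a fixed linear model reaches about 68–76%; at r = 0.3 the figures are 28% and 42%. Most of this loss comes from the 2-point cut. The screening adds about a 19% chance of a spurious covariate and about an even chance of missing a moderately strong confounder, so the added covariates should not be interpreted.

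The documents do not support extending this to all of Aim 2. The dichotomy and the figure of about 40 belong to Aim 2a. Aim 2b shares only the screening rule, does not state how many people its model uses, and makes its main comparisons by t-tests without selection.

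The sizes depend on an assumed screening level, SD of change and set of correlations. The direction does not depend on their exact values. The change is worth making because it improves a named aim at almost no cost; it has no bearing on the primary conclusion.

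**What to change.** **Aim 2a.** Prespecify one linear model in the behavioral arm: 12-week ICIQ-OAB symptom score on baseline ICIQ-OAB, SRTT, card-sort perseverative errors and a short fixed list such as age, gender and MDS-UPDRS part 3. Depression is a listed candidate and may be kept, provided the list is settled before response data are examined. Delete the univariable entry rule. Keep the 2-point responder comparison and its logistic model as descriptive.

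**Aim 2b.** Replace the bivariable screen with a fixed list: the baseline value of the cognitive test analysed, the Anticholinergic Risk Scale score (already named for this model), treatment group if both arms are modelled, age, gender and MDS-UPDRS part 3. State which arms and how many people the model includes.

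**Cost.** SAP wording only. Every variable is already collected. A few degrees of freedom go to covariates that may turn out not to matter.

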The *long term goal* of the PI's research group is to alleviate urinary symptoms as a contributor to disability among Veterans with PD and contribute to understanding of the brain-bladder connection in the setting of neurodegenerative disease. We propose the following specific aims:

Specific Aim #1: Using a RCT, determine non-inferiority of pelvic floor muscle exercise-based behavioral therapy versus drug therapy for urinary symptoms in PD. We hypothesize that pelvic floor muscle exercise-based behavioral therapy will reduce urinary symptom severity with a difference compared to

drug therapy that does not exceed the non-inferiority margin of a validated OAB questionnaire. The primary outcome, OAB severity, will be measured using the OAB symptom questionnaire (International Consultation on Incontinence-OAB (ICIQ-OAB) symptom score) with a non-inferiority margin of 15%.

Specific Aim #2 (mechanistic aim): Determine if domain-specific cognitive function impacts the response to exercise-based behavioral therapy or drug therapy for urinary symptoms.

Aim 2.a. Do higher baseline motor skill learning capacity and executive function scores predict better outcomes in the exercise-based behavioral therapy versus drug therapy group?

Aim 2.b. Compared to exercise therapy, does anticholinergic drug treatment for urinary symptoms worsen executive function and PD motor symptom severity?

Research Design and Methods

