To assess the potential impact on motor symptoms, we will assess the change in the motor symptom subscale of the MDS-UPDRS (part 3 score). Similar to the cognitive testing, baseline and 12-week post-randomization assessments will be evaluated using paired t-tests to assess for change within the drug group and two-sample t-tests for difference across groups, with the behavioral therapy group serving as a control for this analysis. Previous research suggests an increase in the MDS-UPDRS part 3 score of 4.6 points is associated with clinically relevant decline in motor function⁷⁰.

Visit Schedule

Visit 1: Baseline (One phone/telehealth session and one in-person session)

Explanation of study procedures and consent to be a participant

Interview: Demographics, continence and medical history, MoCA, LSA, GDS

Physical: Height, weight, vital signs, cardiac, pulmonary, and abdominal exam, genital and rectal exam, basic neurologic exam, MDS-UPDRS, determination of post-void residual by bladder ultrasound

Laboratory Examination: Urinalysis and BMP and HgbA1c if indicated

Education: How to complete bladder diary, handout take-home questionnaires (ICIQ-OAB and OAB-QOL)

Visit 2 (Part 1) : Randomization

Interview: Collect and review 7-day bladder diary, ICIQ questionnaires

Physical: Vital signs; review laboratory results; determination of post-void residual by bladder ultrasound if not conducted at first visit;

Procedure: **Randomization (Behavioral Therapy or Drug Therapy)**

Behavioral Therapy	Drug Therapy

Visit 2 (Part 2): Behavioral Therapy Randomization
 
Procedure: Neuropsychological battery, SRTT, Pelvic floor muscle exercise training
 
Education: specific behavioral techniques for constipation, modification of fluid intake or timed voiding
	
Visit 2 (Part 2) : Drug Therapy Randomization
 
Procedure: Neuropsychological battery, SRTT
 
Education: Medication

Visit 3: Behavioral Therapy (2 weeks)
 
Interview: Review PFME record, address new problems, reinforce practice at home and verbal feedback regarding muscle control
 
Education: Urge suppression strategy, management of stress-related urine loss (if applicable)
	
Visit 3: Drug Therapy (2 weeks)
 
Interview: Medication Management, Medication Side Effects
 
Education: Medication & Bladder Diary & Forms (to return at Visit 5)

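### Aim 2b's between-arm t-tests omit the baseline score and the stratification factors, and the plan does not say that this contrast, rather than the within-drug paired test, decides the aim

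*Combined protocol and SAP*

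**What the plan says.** The aim is comparative: "Compared to exercise therapy, does anticholinergic drug treatment for urinary symptoms worsen executive function and PD motor symptom severity". Under Aim 2b, Measures, "Participants in both groups will complete a baseline and 12-week neuropsychological battery as previously described", and the MDS-UPDRS is repeated at 12 weeks.

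Under Aim 2b, Data Analysis, the cognitive tests are to be "evaluated using paired t-tests to assess for change within the drug group and two-sample t-tests for differences across groups". The behavioral arm is named as the control. The text does not say whether the two-sample test compares changes or 12-week scores.

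For motor symptoms the variable is clear: "we will assess the change in the motor symptom subscale of the MDS-UPDRS (part 3 score". The tests are again a paired t-test within the drug arm and "two-sample t-tests for difference across groups, with the behavioral therapy group serving as a control for this analysis". The same paragraph cites earlier research that an increase of "4.6 points is associated with clinically relevant decline in motor function".

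One covariate model is planned, for cognition only: "The Anticholinergic Risk Scale score will be included in a multivariable model including baseline characteristics associated with changes in cognitive function in bivariable analyses". It lists neither treatment arm nor the baseline value of the test being analysed.

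The Randomization section stratifies by site, gender, ICIQ-OAB score (cut at 9) and part 3 motor score (cut at 33). None of these enters the Aim 2b t-tests. No alpha, SD, power or detectable difference is given for Aim 2b, and no sentence says which of the two tests answers the question.

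**The concern.** Two separate matters are involved.

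**Precision.** Every Aim 2b outcome is measured at baseline and week 12 in both arms, and baseline motor severity is a stratification factor. A two-sample t-test on week-12 scores ignores the baseline. A t-test on change uses it, but with the slope fixed at 1. ANCOVA estimates the slope and in expectation is at least as precise as either, apart from a small loss of degrees of freedom. The aim looks for harm, so a missed worsening is the costly error, and a test that is less precise than the data allow makes it more likely.

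**Which test decides.** A paired test within the drug arm does not address a comparative question. For cognition it mixes drug effect with practice on a repeated battery, and the plan mentions neither practice effects nor alternate test forms. Because the paired and the between-arm tests are listed side by side without an order, a null paired result could be reported as absence of harm.

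**Working it through.** There is no Aim 2b sample-size or power figure in the plan to reproduce.

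**Inputs from the documents.** 80 completers (Power Analysis) and roughly equal groups (Human Subjects), so n = 40 per arm; 4.6 points on part 3 (Aim 2b, Data Analysis).

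**Assumptions, not in the documents.** Correlation ρ between baseline and week 12 of 0.5 to 0.8; part 3 SD of 10 (range 8 to 12); two-sided alpha 0.05; equal SDs at both times.

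**Step 1: relative variance of the between-arm difference**, with a week-12-only t-test set to 1.
- Change-score t-test: 2(1 − ρ)
- ANCOVA on the baseline score: 1 − ρ²
- ANCOVA relative to change: (1 − ρ²) / [2(1 − ρ)] = (1 + ρ)/2

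**Step 2: power for a 4.6-point difference.** The standard error is SD × √(v × 2/40), where v is the relative variance. Power comes from the noncentral t distribution. At SD 10 and ρ = 0.7:
- Change: v = 0.60, SE = 10 × √0.03 = 1.73, 4.6/1.73 = 2.66, power 75%.
- ANCOVA: v = 0.51, SE = 10 × √0.0255 = 1.60, 4.6/1.60 = 2.88, power 81%.

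| ρ | v, change | v, ANCOVA | ANCOVA ÷ change | ANCOVA ÷ week-12 only | Power, change (SD 10) | Power, ANCOVA (SD 10) |
|---|---|---|---|---|---|---|
| 0.5 | 1.00 | 0.75 | 75% | 75% | 53% | 65% |
| 0.7 | 0.60 | 0.51 | 85% | 51% | 75% | 81% |
| 0.8 | 0.40 | 0.36 | 90% | 36% | 90% | 92% |

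At ρ = 0.7 the move from change to ANCOVA is 91% to 94% for SD 8, and 59% to 66% for SD 12. These figures adjust for the baseline score only; any further gain from the stratification factors is not counted.

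The "ANCOVA ÷ change" column applies to part 3, where the plan names change. For cognition either ratio column may apply, because the plan leaves the variable open.

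**Step 3: practice effects (cognition), in SD units.** Assume a true drug decrement of 0.3, ρ = 0.7 and 40 per arm. The SD of change is √(2 × 0.3) = 0.775, and the standard error of the within-drug mean change is 0.775/√40 = 0.122.

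| Practice gain, both arms | Net drug-arm change | Paired test within the drug arm | Expected between-arm difference in change |
|---|---|---|---|
| 0 | −0.3 | significant decline in about 67% of trials | −0.3 − 0 = −0.3 |
| 0.3 | 0 | significant decline in about 2.5% (chance level) | 0 − 0.3 = −0.3 |
| 0.5 | +0.2 | significant improvement in about 36% | 0.2 − 0.5 = −0.3 |

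The paired result moves with the practice gain; the between-arm difference does not. In a simulation of 10,000 trials with a 0.3 practice gain, the between-arm change test detected the decrement in 41% and ANCOVA in 45%.

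**The case against.** The strongest reply is that the plan already contains the right comparison. Aim 2b is worded as a contrast with exercise therapy, the behavioral arm is named as control for both domains, and both arms take the same battery at the same times. Under randomization a two-sample t-test on change is valid and unbiased. That stands: ANCOVA here is a gain in precision, not a repair of bias, and the passage quoted on the control group is the safeguard.

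Several stronger readings are tempting, and the documents do not support them.

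- *That practice effects will lead the trial to miss harm.* A gain common to both arms cancels in the planned between-arm contrast, and nothing says that the paired test decides. The problem is confined to the paired test on cognition. It does not carry over to part 3, which is a physical examination rated by the investigator.
- *That the motor analysis discards the baseline.* The plan names change in part 3. The 53% power that a week-12-only test would have at SD 10 and ρ = 0.7 therefore does not describe it; the relevant step is 75% to 81%, and it shrinks as the correlation rises.
- *That 4.6 points is a margin or design target.* It is cited as background on clinically relevant decline. It is used above only as a reference size.
- *That cognition has no adjusted analysis at all.* A multivariable model is planned. It is not the missing analysis, though: it names neither arm nor baseline test score, and it selects its other covariates by bivariable screening.
- *That regression to the mean is a major threat.* Eligibility does not select on part 3, and among the tests in the battery only the MoCA has an entry cut-off.

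It is also fair that Aim 2 is labelled mechanistic and claims no power. That limits the weight of the point without removing it.

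**Conclusion.** The point holds as a free improvement. The planned between-arm test is sound but less precise than the data allow, and the plan should say that it, and not the paired test, answers Aim 2b.

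For part 3 the gain is modest: 10% to 25% of variance for ρ between 0.8 and 0.5, or about 6 points of power in the central example. For cognition the gain is the same if change is compared. It is 25% to 64% of variance if week-12 scores are compared, and the text does not settle which. The paired cognitive result cannot be interpreted as a drug effect without an assumption about practice.

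The variance ratios rest on the assumed correlations. The power figures also rest on the assumed SD and alpha, and the practice illustration on assumed gains and decrement. The documents give none of these. That the t-tests are unadjusted, and that no deciding test is named, is read from the text and needs no assumption.

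**What to change.** In Aim 2b, Data Analysis, for each cognitive test and for MDS-UPDRS part 3:

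1. Replace the two-sample t-test with ANCOVA of the week-12 score on arm, the baseline value of the same measure, and the stratification factors as main effects.
2. Report the adjusted between-arm difference with its 95% CI. For part 3, show the interval beside the cited 4.6 points as context, not as a margin.
3. State that the Aim 2b conclusion rests on this contrast, and that the within-drug paired change is descriptive.

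This also removes the ambiguity between change and week-12 scores for cognition. Once the baseline score is a covariate, the estimated arm effect is the same with either as the outcome.

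The cost is SAP wording, best settled before outcome data are examined. All the covariates are already collected, and no visit, measurement or sample-size change is needed.
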